Recruitment. Given the inclusion criteria and site volume for the pilot, we expect to recruit 15 youth per arm (intervention and attention control) session for a total of 3 cohorts of 15 in each arm or 6 total groups. Based on what we've learned from previous studies with YEH, we will recruit 90 youth to deliver the intervention or control to at least 60 youth. Youth will be recruited primarily from Covenant House Texas (CHT), and homeless shelters and drop-in centers if additional recruitment sites are needed, to participate in the pilot. Youth who are eligible and enroll in the pilot study will complete a baseline survey, attend 5 90 minute sessions, complete very brief pre-post session surveys, as well as follow-up surveys immediately post-intervention and at 3 months post-intervention. Approximately 22% (n=20) of the pilot study participants will be recruited to also participate in a post-intervention exit interview. Participants will have the phone for the duration of the study. The intervention is informed by the Risk Amplification Model (RAM) and the Minority Stress Model (MSTM) and will be fully developed in Years 1-2 using a systematic intervention development process; Plan, Do, Study, and Act. In order to ascertain the feasibility and acceptability of the intervention (Aim 3), we will obtain participant feedback via exit interviews as well as quantitative implementation indicators (e.g., refusal rate, completion rates, and survey measures).

Inclusion/Exclusion of Service Providers. Key Informant Interview participants (n=12) and Expert Advisory Panel service provider members (EAP, n=8) will be health and social service providers for YEH recruited from local shelters (i.e., resident advisors, in-take specialists), drop-in centers (i.e., social workers, case managers), homeless healthcare clinics (i.e., nurses, mental health counselors, patient navigators), and the Homeless Youth Network (a network of YEH providers, of which [name] is an active member). Providers will be considered eligible if they are currently providing health or social services to YEH and are interested in participating in an interview or as a member of the Expert Advisory Panel. For those providers interested in the EAP, they will be considered eligible if they anticipate being able to meet for the regularly scheduled meetings at least 75% of the time.

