Expected Outcome. The result of Aim 1 activities will inform how to tailor .b to the lived experience and needs of sheltered YEH. The essence of .b will remain though we anticipate tailoring it to be 5-sessions

in order to approximate the average length of stay for YEH in the shelter. The tailored *b* will retain common domains (i.e., analytical, somatic, grounding, visualization, and awareness) while tailoring the content and delivery to sheltered YEH. Subsequently, we will conduct iterative pre-pilot beta testing of sessions with the HYWG to finalize content and delivery methods and strategies based on user feedback.

Specific Aim 2. Optimize RCT outcome measures using cognitive interviews with the HYWG (n=10)

Cognitive Interviews. As part of the FGDs, we will field test the proposed outcome measures to assess understandability and participant burden allowing us to determine the optimal measures for the RCT. We will assess various ways to measure mindfulness app usage including self-report and app-based reports.

Proposed Measures. Baseline measures will include demographics (i.e., age, gender identity, race/ethnicity, sexual orientation, educational level, and employment). We will assess historical factors such as involvement in the foster care and juvenile justice systems, adverse childhood experiences,¹⁴² victimization,¹⁷⁹ age at first homelessness, and length of current homelessness. We will include psychosocial wellbeing measures, including mindfulness; self-compassion; social connectedness; stress, anxiety, depression, psychological distress, affect, and vulnerability symptoms; and inhibition, impulsivity, and risk behaviors (see Table 2). Finally, we will test several ways of measuring mindfulness app use including self-report use and app use summary data obtained on the study phone such as the one from the CALM or Headspace app.

Table 2. Potential Outcome Intervention Measures for Pilot Testing

Construct	Possible Scales to be Included	Psychometrics
Emotion Regulation	Difficulties in Emotion Regulation Scale ¹⁴³	$\alpha = 0.72-0.87^*$
Mindfulness	Child and Adolescent Mindfulness Measure ¹⁴⁴ ; Cognitive and Affective Mindfulness Scale-Revised ¹⁴⁵ ; Mindful Attention Awareness Scale ¹⁴⁶	$\alpha=0.82^{**}$
Self-Compassion	Self-Compassion Scale ¹⁴⁷	$\alpha=0.91^{**}$
Social Connectedness	Social Connectedness Scale; Interpersonal Support Evaluation (ISEL-12) ¹⁴⁸	$\alpha=0.91, 0.77^*$

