Purpose. The purpose of this pilot study is to examine intervention feasibility and acceptability and determine effective recruitment and retention strategies, randomization processes, participant tracking and follow-up procedures, retention benchmarks, and evaluate the feasibility of outcome measures. To this end, we will conduct this feasibility trial using a two-group randomized attention control trial design.

Intervention Delivery. Drs. [name] and [name] are certified teachers of existing youth-focused MBI curricula, *.b*⁸⁹ ([name], [name]), and *MBSR-T*¹⁰⁸ ([name]), and will work with the interventionist if issues arise during intervention delivery. Additionally a fidelity checklist will be made to assess the delivery of the tailored *.b*. While the session length, group size, and session spacing will be informed by the PDSA work with the HYWG and finalized in the formative phase, we describe our estimates below. We anticipate between 4 and 5 intervention sessions that will last between 60-90 minutes. Each cohort will include approximately 10-15 youth. Based on attendance at our recent pilot *.b* program, we plan to recruit 15 youth to have an average final group size of 10 youth depending on HYWG preferences and PDSA data. We anticipate having 6 cohorts of youth (3 intervention and 3 attention control). Each session will likely include brief didactic presentations, videos, and mindfulness practice followed by inquiry. We anticipate that sessions will take place twice a week. Sessions will be held on site at the CHT shelter in a quiet, designated learning space to ease access to sessions for the participants and to assure access to shelter staff (e.g., social workers and case managers) and services (e.g., food and shelter). CHT has onsite, weekday clinical and mental health care and established protocols for accessing needed resources 24/7. Selection criteria for the interventionist include maintaining a personal mindfulness

practice for at least two years, trained in .b, and prior experience working with high-risk youth. The interventionist will receive additional training in Trauma-Informed Care as well as study procedures.

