Enrollment and Data Collection Procedures. The RC and RA will recruit and enroll all participants. Once consented, the youth will take the baseline survey and receive their group assignment from the RC. A computerized randomization generator will be used. The RA will be blinded to group assignment and will conduct all data collection. For the purpose of this study, enrollment will be defined as completing consent, baseline survey, and at least one lesson of the intervention or control condition. Surveys will be completed by participants on iPads using REDCap. Participants will enter response data directly into the tablet so their answers will be private. In the case of electronic device failure, we will use back-up iPads and paper surveys and the RA will enter the responses into REDCap within 24 hours. We will use unique study IDs in the place of names to protect participant confidentiality. **Baseline and Follow-up Surveys.** Participating youth will complete surveys at baseline, immediate post-intervention, and at 3- and 6-months post-intervention. Surveys will take approximately 30 minutes to complete and will include items to measure mindfulness, perceived stress, emotion regulation, impulsivity, and mental health symptoms (see Table 2 for example measures and psychometric properties) and youth risk behaviors. We will also pilot self-report and app use to determine the most effective way to measure use of commercially available mindfulness apps. Data usage information will be gathered from mediation app on participants' phone. **Pre- and Post-Session Surveys.** Very brief pre- and post-session brief surveys will capture real-time stress, emotion regulation, positive and negative affect, mindfulness, impulsivity, and session feedback (post-session only) including likability of session content, delivery format, length, and delivery timeframe. These surveys will take approximately 5 minutes to complete prior to and immediately after each session. **Exit Interviews.** The RC will conduct individual or group exit interviews with 20 youth from the pilot study participants that will be audio-recorded and take about 30-45 minutes. We will randomly select participants from each of the 4-6 intervention cohorts to have equal representation by gender identity, age, and study group. We will elicit participant feedback on study procedures, intervention acceptability, delivery methods and strategies, barriers and facilitators of

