session participation, mindfulness skills practice, measures completion, and overall experience with the intervention and the study. While the exit interview guide will be finalized during YR-1 with the assistance of the HYWG, we anticipate querying the participants about: 1) what the participant thought of the number and type of questions asked in the baseline, pre-post session, and initial follow-up survey, 2) thoughts on the intervention sessions (e.g., content, length, delivery mode, frequency/spacing, perceived impact), and 3) any other comments about the intervention or study procedures including a comparative analysis¹⁸⁰ of the commercially available mindfulness apps. Participants will receive an additional \$10 gift card for a local restaurant or grocery store for completing the exit interview.

Table 3. Feasibility and Acceptability Benchmarks

Construct	Measure	Benchmarks
Recruitment feasibility	# screened & enrolled/mo; time delay from screening to enrollment; average time to enroll sufficient class size; appropriateness of exclusion criteria screening process	Enroll 50% of screened and eligible participants; <2-week delay from screening to enrollment; <2 weeks to enroll sufficient class size; <5% inappropriate exclusion/inclusion
Retention feasibility	3- and 6-mo follow-up survey completion; compare intervention vs. control group	At least 50% retained at 3 and 6-mo; <15% group retention differential
Treatment adherence	Attend all sessions; perform the intervention; complete study measures	At least 50% of participants in each cohort will attend at least 3 of 5 scheduled group sessions ^{108,164}
Treatment delivery fidelity	Session delivery fidelity checklist	At least 70% of each session content is completed
Completeness of assessment data	Data from surveys, focus groups, and key informant interview are complete and intact	Less than 50% data loss or incompleteness
Acceptability	Credibility/expectancy questionnaire ¹⁸¹	Average score of >30

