Recruitment and Retention Plan. Participant recruitment will begin after obtaining UTHealth IRB approval. Our team has received IRB approval for several studies involving interventions with vulnerable populations of young people including young adults and minors experiencing homelessness and mindfulness interventions. To recruit YEH, flyers describing the study will be posted in the common area of local shelters, drop-in centers, and clinics as homeless youth often access services from multiple service providers and locations. We will pass out study information during street outreach events hosted by the partnering agencies. Local healthcare for the homeless providers, The Homeless Youth Network, and the Coalition for the Homeless will be informed about the study and flyers will be posted at local clinics with permission as well as coordinated access housing first locations (where youth can access housing services). Project staff will also approach youth who receive services at the Salvation Army drop-in center and Covenant House Texas shelter to screen for eligibility. Additionally, participants can contact research staff after seeing the flyers at other shelters, drop-in centers, or healthcare for the homeless clinics. The research staff will work with the shelter staff to identify youth at the site each day who may be eligible. We will recruit participants three days a week during regular business hours at the shelter and drop-in centers and during street outreach until we have reached our final sample size. The research staff will maintain a consistent presence at the agencies and will approach young people who present. In the event that the common room in the shelter or drop-in center is crowded, they will ask to speak to identified youth in a private office. The research staff will explain the study and complete the informed consent process with interested youth. All prospective participants will be assured that study participation will in no way affect their health and social services. Informed consent and contact information will be obtained from participants.

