Role of NIH. Summaries of the protocol and design, status of intervention group, and data collection procedures, summary of subject contacts, discussion of any adverse reactions or any potential adverse reactions, status of data entry and verification, a summary of any descriptive statistics to date, and the recommendations of the monitoring board will be included in each annual report to NIH. In addition, should any adverse reaction occur or should the monitoring board recommend early termination of the study, the information will be immediately reported to the program officer at NCCIH.

Statistics

Fifty six YEH will participate in the focus groups during the first 2 years of the study to Tailor .b and finalize the attention control condition. Sixty YEH will participate in the pilot RCT.

Sample Size for Pilot RCT. We will recruit 90 YEH with equal randomization into the intervention and attention control arms to reach the target of 60 YEH completing the intervention and control conditions. The sample size is based on practical considerations regarding the number of participants needed to assess feasibility and acceptability outcomes and not on the performance of inferential statistical analyses. However, a final sample size of 60 youth completing the pilot will have 80% power to detect a medium effect size of 0.74 for stress response.¹⁸²

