Participant recruitment will begin after obtaining UTHealth IRB approval. Our team has successfully been approved to conduct similar studies among YEH recruited and followed-up in the same fashion. Flyers describing the study will be posted in the common area of CHT, local drop-in centers, and shelters as homeless youth often access services from multiple service providers and locations. Local Healthcare for the Homeless providers and the Coalition for the Homeless will be informed about the study and flyers will be posted at local clinics with permission. Project staff will approach youth who receive services at CHT to screen for eligibility. Additionally, participants can contact research staff after seeing the flyers at other shelters, drop-in centers, or Healthcare for the Homeless clinics. The research staff will work with the shelter case managers to identify youth at the site each day who may be eligible. We will recruit participants three days a week during regular business hours at the shelter and drop-in centers for two weeks prior to the beginning of each group session and the research staff will maintain a consistent presence at the recruitment sites. The research staff will approach young people present at the recruitment sites. In the event that the common room in the shelter or drop-in center is crowded, the research staff will ask to speak to identified youth in a private office or the library meeting area. The research staff will explain the study and complete the informed consent process with interested youth. As part of the consenting procedures, each youth will be asked to provide a separate signature of consent if they are interested in being contacted for an exit interview. All prospective participants will be assured that study participation will in no way affect their health and social services. Informed consent and contact information will be obtained from participants. These procedures for recruitment were developed and proved successful in our prior qualitative, cross-sectional, and mindfulness pilot studies with homeless youth and have been used at the same sites we will use in this study to recruit participants.

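### The intake forecast, the two recruitment patterns and Table 3's two-week benchmarks do not agree, so youth assigned soon after consent may wait weeks for lesson 1

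*Combined protocol and SAP*

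**What the plan says.** All references are to the combined protocol and SAP.

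- **Order of steps** (Specific Aim 3, Enrollment and Data Collection Procedures): "Once consented, the youth will take the baseline survey and receive their group assignment from the RC". No batch assignment, block size or waiting list is described. The same section counts a youth as enrolled only after consent, the baseline survey and a first lesson in either arm.
- **Allocation** (Statistics, Sample Size for Pilot RCT): "We will recruit 90 YEH with equal randomization into the intervention and attention control arms".
- **Class size** (Study Population, Recruitment): "we expect to recruit 15 youth per arm (intervention and attention control) session for a total of 3 cohorts of 15 in each arm". Intervention Delivery allows somewhat smaller groups: "Each cohort will include approximately 10-15 youth". Attention Control Condition matches the control classes to the intervention classes on group size and timing, among other features.
- **Forecast intake** (Potential Problems and Alternative Strategies): 18 participants per two months, said to give all 90 within five months.
- **Recruitment pattern, first description** (Recruitment and Retention Plan): three days a week at the shelter and drop-in centers and "during street outreach until we have reached our final sample size".
- **Recruitment pattern, second description** (Ethics, paragraph on participant recruitment): three days a week "for two weeks prior to the beginning of each group session".
- **Benchmarks** (Table 3, recruitment feasibility): "<2 weeks to enroll sufficient class size", and also less than two weeks from screening to enrollment.
- **Course length** (Specific Aim 1, Expected Outcome): five sessions are anticipated "in order to approximate the average length of stay for YEH in the shelter". The stay is not given in days.

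**The concern.** With individual 1:1 assignment and matched classes, a pair of classes needs about 30 randomised youth before both can start at the recruited size of 15, or 20 at the lower size of 10. If youth are surveyed and assigned as they consent while the pool builds slowly, there is a gap between baseline or assignment and lesson 1.

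Two things are at stake. First, this pilot exists to measure recruitment, adherence and retention for a larger trial. A benchmark missed because of the intake schedule could be read as a failing of the intervention. Second, the gap falls after randomisation in a mobile population. A youth who leaves before a first lesson is randomised but, by the protocol's definition, not enrolled. Depending on the denominator, that youth is either a post-randomisation loss or disappears from the count. For youth who stay, baseline stress and mood may be weeks old when exposure begins.

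**Working it through.** **Inputs.** Intake of 18 per two months, or 90 in five months (Potential Problems and Alternative Strategies); classes of 15 or, at the low end, 10 (Recruitment; Intervention Delivery); 1:1 allocation (Statistics); two-week limits (Table 3). One month is 365.25/12/7 = 4.348 weeks. Arrivals are assumed steady.

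**Step 1: the plan's own forecast.** 18 per two months is 18/2 = 9 per month. Then 9 × 5 = 45 youth in five months, and 90/9 = 10 months for the full sample. The stated five months needs 90/5 = 18 per month. The forecast does not reproduce as written, so both rates are carried forward.

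**Step 2: youth arriving in two weeks.** 9 × 2/4.348 = 4.1; 18 × 2/4.348 = 8.3.

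**Step 3: time to fill a matched pair.** Fill time = n/rate × 4.348 weeks. Mean wait = (n − 1)/(2 × rate) × 4.348 weeks. Share waiting under two weeks = 2/fill time.

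| Rate per month | Youth needed | Fill time (weeks) | Mean wait (weeks) | Share waiting under 2 weeks |
|---|---|---|---|---|
| 18 | 30 (15+15) | 7.2 | 3.5 | 28% |
| 18 | 20 (10+10) | 4.8 | 2.3 | 41% |
| 9 | 30 (15+15) | 14.5 | 7.0 | 14% |
| 9 | 20 (10+10) | 9.7 | 4.6 | 21% |

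Fill time is roughly the wait of the first youth in the queue; the typical wait is the mean.

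**Step 4: a more lenient reading of the benchmark.** If only one class must fill, ignoring the other arm, 15 youth take 15/18 × 4.348 = 3.6 weeks or 15/9 × 4.348 = 7.2 weeks. Ten youth take 2.4 or 4.8 weeks. All exceed two weeks, the most favourable case by little.

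**Step 5: screening to enrollment.** Because enrollment requires a first lesson, the wait for a class counts towards this delay. Every mean wait in Step 3 (2.3 to 7.0 weeks) exceeds the two-week limit.

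**Step 6: the two-week window.** Filling 30 places in two weeks needs 30/2 = 15 youth per week, or 15 × 4.348 = 65 per month. That is 65/18 = 3.6 or 65/9 = 7.2 times the forecast rate. At three recruiting days a week the window has six days, so 30/6 = 5 youth per day. If intake is 18 per two months with one window in that period, at most 18 youth are available, short of the 20 for a 10+10 pair.

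**Sensitivity.** The allocation method is described only as a computerized generator. Under unrestricted 1:1 randomisation, simulation gives an average of about 34 youth before both arms reach 15, so the fill times above would lengthen.

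**The case against.** The strongest reply is that the plan already contains the remedy. Recruiting only in the two weeks before each group would cap the wait at about two weeks and fits Table 3. Recruiting until the sample is full may be just the overall stopping point, reached through successive windows. On that reading intake comes in bursts, and steady arrivals are the wrong model. At 18 per month overall, three bursts of 30 spaced 30/18 × 4.348 = 7.2 weeks apart fit five months. The attached timeline shows three entries of 30, although its rows are not reliably aligned in the text available. The protocol also reports recruiting 434 youth in four weeks in an earlier project and a large volume at the site.

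Much of this stands. The two recruitment descriptions can be made compatible, and 30 youth in two weeks is not shown to be impossible. But no section plans 15 per week for this trial, the 434 came from a different study, and the lower stated rate cannot fill a pair in one window. The forecast's arithmetic is wrong on any reading.

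Other fair points:

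- The enrollment text gives an order of steps, not same-day timing. Assignment soon after consent is the natural reading, but an inference.
- The forecast counts enrollments, which require a lesson, so consents could run higher. They would still need to be 3.6 times the higher rate to fill 15+15 in two weeks.
- Recruiting 90 to obtain 60, tracking, and transport vouchers soften losses. However, the provision for youth who leave the shelter applies to those resident when enrolled. It does not clearly cover someone who leaves before a first lesson.

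A reader might infer that every youth waits 7 to 14 weeks, that the wait outlasts the shelter stay, or that leavers will be scored as non-adherent. The documents support none of these. The first is the fill time; the mean is about half. The stay is never given in days. Five sessions at two a week suggest 2 to 2.5 weeks, but that is an inference from provisional figures, and the mean wait for 10+10 at 18 per month (2.3 weeks) falls inside that range. Table 3 does not say how youth who leave before lesson 1 are counted.

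**Conclusion.** The point holds as a set of inconsistencies to reconcile. The intake forecast is wrong by a factor of two (ten months rather than five at the stated rate). Under steady arrivals at either rate, the two-week class-fill benchmark is missed for a matched pair at either class size, and the mean wait exceeds the two-week screening-to-enrollment benchmark. A pair of 15+15 fills in up to 7.2 or 14.5 weeks, with mean waits of 3.5 or 7.0 weeks; a pair of 10+10 fills in 4.8 or 9.7 weeks, with means of 2.3 or 4.6.

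These figures rest on constant arrivals, balanced assignment and both classes starting together. A two-week window that actually filled would limit the wait to about two weeks. Whether the wait exceeds the shelter stay cannot be shown. What does follow is that some youth may wait weeks after baseline or assignment, and that the plan does not say how those who leave in the gap are counted.

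**What to change.** 1. In Potential Problems and Alternative Strategies, correct either the rate or the duration.
2. Use one recruitment pattern in the Recruitment and Retention Plan and in the Ethics recruitment paragraph. Restate Table 3's class-fill benchmark or the intake forecast so that they agree, and say whether a sufficient class means one class or both.
3. Consent youth during the pre-class window, then take the baseline survey and run the 1:1 assignment for the whole pool in the final days before session 1.
4. Report days from baseline and from assignment to session 1. Count every randomised youth who never attends a lesson, alongside adherence and retention.

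Items 1 and 2 are wording changes. Item 3 reorders existing steps and adds no visits, but it concentrates work: 30 surveys in two to three days is 10 to 15 per day. The protocol should disclose that burden and spread the surveys over enough days to be workable. Some consented youth will leave before assignment; they would appear in the recruitment figures only. Item 4 needs only dates and attendance records.
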